QMT= Quantitative Muscle Testing
RM = Magnetic Resonance
RX= radiography
VIT D= Vitamin D
VR= Residual Volume

3. Responsibility (role of the study promoter and of researchers)

Main researcher: [name] Collaborators: [name], graduated with [name] and now attending the first year of school in medical genetics at the Fondazione IRCCS Cà Granda, Ospedale Maggiore Policlinico. She will collect clinical charts and report clinical data to analyze in a excel file that will be used for the statistics. [name], Director of the Neuromuscular and rare Disease Unit

4. Emendamenti ed altre modifiche al protocollo Not relevant.

5. Timelines Planning: start of data collection: June 2020. End of data collection: September 2020
Final report: December 2020

6. Rational and background

LGMD2E is a rare type of a hereditary muscular dystrophy transmitted in an autosomic recessive manner. This disease is determined by the presence of mutations involving the Beta Sarcoglycan gene, coding for a protein which is involved in the stabilization of the glycoprotein complex

associated to dystrophin (1). The main role of beta Sarcoglycan only partly explains the severity of the clinical phenotype reported in these patients compared with other LGMD (2). LGMD 2E debuts in early childhood, involving skeletal muscles with a progressive centripetal trend that in last stages affects also respiratory and cardiac muscles (3). The early onset and the severity of the disease affecting cardiopulmonary apparatus, make this disease very close to the more famous and studied Duchenne Muscular Dystrophy (4). More than 60% of LGMD 2E patients suffer from heart failure (5), not less common is the involvement of respiratory system which insufficiency represents the main cause of death in these patients (6). Unfortunately, because of its rareness, literature is poor of data about this disorder and no natural history study have ever been reported until now. Lacking similar studies, therapeutical and clinical management is not easy and often based on studies investigating other subtypes of muscular dystrophies, often more benign.

Furthermore, we have little knowledge about possible genotype-phenotype correlations for this disease (7). We do believe that a natural history study might help us to improve our knowledge of this condition's evolution, leading to the design of specific guidelines for the follow up of these patients, both under the therapeutical and clinical point of view.

Guidelines will uniform the clinical approach to this disease, both on the National and the international scenario, and will improve the use of sanitary resources. Furthermore, with a phenotype-genotype correlation study, it will be possible to recognize those patients that are more at risk to develop a more severe disease.

7. Research query and objective

The lack of data on natural history of this rare disease and the need to define guidelines for the best follow up of these patients, compelled us to set up this study. In this study any investigation performed in patients affected by LGMD 2E will be considered with the aim to recognize the progression of the disease and those variables that are more useful and precise in describing its evolution. Primary objective of the study is to obtain more and better knowledge of this rare group of LGMD, describing its natural history through the analysis of clinical charts of the more affected patients possible.

To select clinical variables that are more useful to define the evolution of the disease and to identify any possible differences in clinical presentation that might be due to differences in genotype-phenotype correlation. Secondary objective of the study is to demonstrate the real impact of cardiopulmonary impairment on the prognosis of these patients.

Thank to these knowledges, to lead to a better therapeutic approach to this disease, stimulating the development of new drugs.

8. Methods

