8.2 Setting

Patients followed by the ambulatory of neuromuscular disorders of Centro Dino Ferrari, Padiglione Monteggia of Fondazione IRCCS Ca' Granda Ospedale Maggiore Policlinico (Unit of Neurology), will be recruited during the ordinary follow up routine or will be reached out to participate to this study. Furthermore, thank to the sponsorship of Gruppo familiari beta sarcoglicanopatie (GFB), more patients that are in the network of this association will be reached out from the PI of the study and eventually included. Data will be provided by patients themselves during the visit at the room number 17 of Padiglione Monteggia of Fondazione IRCCS Ca' Granda Ospedale Maggiore Policlinico (Unit of Neurology). If the patients won't be able to move and will be interested in participating to the study a collaborator of the main researcher will reach the patients at his residence to recruit him. Main source of data will be the clinical chart of the patient and all his clinical documents assessing any operation, ascertain, visits performer through the years until this moment. Main centre will be the Fondazione IRCCS Ca' Granda Ospedale Maggiore Policlinico (Unit of Neurology). Data collection will last six months and later data will be studied.

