8.2.4 Patient participation

Patients might be asked to give to their physician their clinical charts in order to evaluate the visits and investigations performed through the years, also in other hospitals.

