8.3 Variables

Will be extract from the clinical charts of these patients, after the sign of the informed consent for the data management, only retrospective data (therefore all those data older than the day of the recruiting visit).

These data will be reported in a excel file specifically created. On this file data will be anonymized through a patient identification code that will be decrypted in another separate file. For this file will be considered the following data:

a) Dati anagrafici:

1. Anonymized name
2. Sex
3. Age

Form 2- DIAGNOSIS:

- 1) Age at onset
- a) clinical presentation
- b) clinical progression
- 2) CK at onset
- 3) EMG

4) Biopsy:

- a) Histology
- b) Immunohistochemistry
- c) Western Blot

5) Genetic:

- a) In frame del/dupl
- b) Out of frame del/dupl
- c) Missense
- d) Nonsense

Form 3- CLINICAL DATA AND TREATMENTS:

Hospitalization: Data – Cause – Frequency* Surgery: Data – Complications* Fractures: Data – Frequency – Location* Fell: Data – Frequency* Emergency Room Accesses: Data – Cause*

APPARATUS

Skeletal-Muscle

1) Clinical tests:

NSAA* MFM* QMT* Brook Scale* Egen Klassifikation* Barthel Index* Walton and Gardner* & Medwin GSGC* Grip Strength (quantitative)* Handheld Dynamometry* Performance of the Upper Limb Module for DMD 2.0* 10m Walk: 1- normal, 2- slightly impaired- 3 moderately impaired- 4- impaired- 5 with device - 6 not walking but stands- 7 wheelchair 6MWT* time to rise from the floor* Climb 4 stairs (1 no help - 2 one hand on the leg – 3 two hands on the legs - 4 stand with help -5 Handrail - 6 hardly climbs- 7 Not able). 10m Run

Time to rise from a chair (1 Normal - 2 with difficulties -3* helping with one hand - 4 Helping with two hands - 5 other helps - 6 Impossible). Time to stand from the floor (1 Normal - 2 first rise the pelvis and then one hand on the floor - 3 First rise the pelvis and then two hands on the floor - 4 One hand on the leg - 5 Two hands on the legs - 6 Other help - 7 Impossible).

Neuromuscular evaluation (date): maximal voluntary strength: bilateral knees extension, Isometric contraction test*, bilateral knee flexion, Workspace volume

2) Exams:

CK* Muscular RMN

3) Symptoms:

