2) Blood tests: Glucose* Proteins* Hemoglobin* White blood cells* Neutrophils *INR* RATIO* CPK* LDH* Amilase* Cistatine C* AST * ALT * ALP * GGT * Bilirubin total/direct/ indirect* Creatinine* Electrolytes (Sodium – Potassium - Clorum – Calcium total/ionized)* Urine (macroscopic view - blood (Yes/No) – anomalies)*

3) Bone status: MOC - PTH pg/mL - VIT D1,25 pmol/L-VIT D 25 nmol/L*

4)Glycemic state: Insuline - Hb1aC* Pro BNP*

Autoimmune disease

Name*

Treatment*

Therapy

1) Name - posology – data – rationale

2) Prescriptions*

3) Pain therapy*

4) Steroids*

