8.7 Data analysis

Analysis will be performed using generalized linear regression models suitable both for continuous variables both for independent ones. Variables with a nonlinear distribution will be transformed in logarithmic scale before the analysis to be performed. For any analysis data will be divided according to the age of the patient at the moment of the evaluation. Data will be analyzed with linear correlation both compared to the variable age both in bivariate models and multivariate models. Results obtained will be adjusted for confounding factors not related to muscular dystrophy.

Data of included patients will be globally studied and divided in two groups homogeneous for genotype.

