8.7.1 Primary endpoints: analysis

- To obtain a variables distribution according to patients' age and to verify possible correlations with the disease's progression.
- To study possible correlation between variables identified.
- To evaluate possible connections with clinical outcomes

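### The age distribution of examination results is drawn from whoever was tested and the data form records no reason for testing, so symptom-driven testing would overstate cardiac and respiratory findings by an unknown amount

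*Protocol*

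**What the plan says.** The protocol casts its net wide. Section 7 states that "any investigation performed in patients affected by LGMD 2E will be considered". On sources, 8.2 says: "Main source of data will be the clinical chart of the patient and all his clinical documents". Under 8.2.4, patients may be asked for their charts in order to "evaluate the visits and investigations performed through the years, also in other hospitals".

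On analysis, 8.7 states: "For any analysis data will be divided according to the age of the patient at the moment of the evaluation". The first primary analysis in 8.7.1 is "To obtain a variables distribution according to patients' age". Among its aims, 8.7.2 lists choosing the variables to watch during follow-up and possibly identifying examinations that can be dropped.

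The form in 8.3 asks why for some items: "Emergency Room Accesses: Data – Cause" for emergency visits, a cause for hospitalisations, and "Name - posology – data – rationale" for therapy. It lists no such field for echocardiogram, Holter, heart MR, polysomnography, MIP/MEP or pro-BNP.

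Two other provisions bear on the point. Section 8.5 admits only yearly-visit data to the linear correlation and multivariate models. Section 8.7 adjusts for confounders that are unrelated to the dystrophy.

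**The concern.** In a retrospective chart study, who is tested at a given age is decided by past clinical practice and not by the study. If a complaint or a previous abnormal result makes a heart or lung test more likely, patients with involvement are over-represented among those with a result. A distribution by age among the tested then differs from the distribution among the patients who were under follow-up at that age.

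Two conclusions of the study would be affected. One is the description of cardiac and respiratory findings by age, a central part of the natural history. The other is the judgement under 8.7.2 on which examinations are useful: a test done mainly in affected patients is abnormal more often than one done in everybody, and so looks more informative.

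This is a matter for the protocol because 8.3 itself fixes the form. If the reason is not noted while the chart is open, an analysis plan cannot restore it without a second extraction.

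**Working it through.** There is no planned figure to reproduce. The protocol gives no testing rates and no expected share of abnormal findings by age. The 33 patients in 8.5 are a count of those followed over ten years, not the result of a calculation. The check therefore has two parts: what the text allows, and how large the effect would be under stated assumptions.

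**What the text allows**

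- *Age distribution (8.7.1).* No restriction by reason for testing is stated, and the yearly-visit rule is not repeated there.
- *Correlation with age and multivariate models (8.5, 8.7).* The yearly-visit rule applies. The text leaves open whether it means scheduled visits or only a minimum frequency of data.
- *Adjustment (8.7).* It covers only factors not related to the dystrophy. Testing prompted by symptoms of the dystrophy is outside it.
- *Quality control (8.8).* Charts are sorted by type of assessment and by centre, not by reason.
- *Limitations (8.9).* This source of bias is not named.

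**Size at one age, for a yes/no finding**

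Let p be the true share affected and r the testing probability in affected patients divided by that in unaffected patients. Both are assumed. Then

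observed share = p·r / (p·r + 1 − p).

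| p | r = 1 | r = 2 | r = 4 |
|---|---|---|---|
| 0.10 | 0.10 | 0.20/1.10 = 0.18 | 0.40/1.30 = 0.31 |
| 0.20 | 0.20 | 0.40/1.20 = 0.33 | 0.80/1.60 = 0.50 |
| 0.60 | 0.60 | 1.20/1.60 = 0.75 | 2.40/2.80 = 0.86 |

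At r = 1 there is no bias.

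For scale, the 95% half-width with all 33 patients tested and p = 0.20 is 1.96 × √(0.20 × 0.80 / 33) = 0.136. The excess at r = 2 is 0.333 − 0.200 = 0.133, about the same. A confidence interval shows the first error and not the second.

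**Age curve and the yearly-visit rule**

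A simulation of 100,000 patients assumed onset at mean age 20 (SD 7), an exponential symptom lag with mean 3 years, and follow-up ending uniformly between ages 10 and 40. The yearly testing probability was q without symptoms and qs with symptoms. The frequency reading of the rule kept a test only if there was another in an adjacent year.

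| q, qs | True share at 20 | Observed, no rule | Observed, rule read as frequency |
|---|---|---|---|
| 0.3, 0.3 | 0.50 | 0.51 | 0.50 |
| 0.3, 0.6 | 0.50 | 0.63 | 0.73 |
| 0.3, 0.9 | 0.50 | 0.71 | 0.82 |

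Read as a frequency requirement, the rule increases the excess, because patients tested often are more likely to be symptomatic. Read as scheduled visits only, it drops the symptom-ordered tests. Without the rule, the observed curve reaches 50% at age 18 (qs = 0.6) or 17 (qs = 0.9), against a true median onset of 20.

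The age at a patient's first abnormal test moves the other way. Without the rule, it came on average 1.4 years (qs = 0.6) and 1.1 years (qs = 0.9) after true onset.

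**The case against.** The strongest reply is that this is a general caveat of chart reviews and that nothing in the protocol shows testing driven by symptoms. Clinic patients are described in 8.2 as seen during ordinary follow-up. This stands as far as the direction and the size go: both are conditional. It does not remove the gap. Section 6 says that management of this disease often leans on studies of other dystrophies, and disease-specific guidelines are still to be written, so uniform past testing across hospitals cannot be assumed.

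Other parts of the reply also have weight:

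- *The yearly-visit rule may already protect the analysis.* It covers the correlation with age as well as the multivariate models. A reader might infer from section 7 that every examination ever done enters every age analysis; 8.5 contradicts that. The rule protects those models only if it means scheduled visits, and it is not stated for the age distribution.
- *Symptoms are collected beside the tests.* Section 8.3 lists palpitations, syncope, oedema, dyspnoea and sleep complaints, and causes of hospital contacts. Part of the reason for testing can be pieced together from these. They are not tied to a particular examination, however, and do not say why it was ordered.
- *The outcomes are defined differently.* The cardiac and respiratory outcomes in 8.4 are ages at first drug or device, not positive tests. A reader might infer that these are biased by the mechanism described here; the documents do not support that.
- *Restricting to scheduled examinations has its own bias.* It could under-represent affected patients once their testing becomes symptom-led, and it would thin out a cohort of about 33. This is a good reason not to make it the main analysis.
- *The formula is for a yes/no finding.* It does not give the bias for continuous measures such as ejection fraction or MIP/MEP.

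**Conclusion.** The point holds in a limited form. The age distribution of examination results under 8.7.1 rests on whoever was tested, the form does not record why, and nothing planned corrects for it. If affected patients are tested more often, the share with abnormal cardiac or respiratory findings at a given age, and the apparent usefulness of rarely done tests, will be overstated. With an assumed true share of 20% and testing ratios of 1, 2 and 4, the observed shares are 20%, 33% and 50%. All of these inputs are assumptions; the documents give no basis for choosing among them.

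A reader might go further and infer that involvement will be shown as both more frequent and earlier. The documents do not establish this. The curve among those tested may shift to younger ages, but the age at a patient's first abnormal test tends to be late, and with equal testing the share is not inflated at all. The point is worth settling before extraction, because the missing information is cheap to note then and hard to recover afterwards.

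**What to change.** - In 8.3, add to each dated examination a field with three values: *scheduled follow-up*, *prompted by symptoms or findings*, *unknown*.
- Keep all examinations as the main description in 8.7.1. For each variable and age band, report the number of patients tested over the number under follow-up.
- Repeat the age distributions on scheduled examinations as a sensitivity analysis.
- State in 8.5 whether a yearly visit means a scheduled visit or a minimum frequency of data.
- Name testing by indication as a limitation in 8.9, and take it into account when judging examinations under 8.7.2.

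The cost is one more entry per examination during extraction and a few sentences of text. Charts from other hospitals will leave a share of unknowns, and for rarely done tests the sensitivity analysis will rest on few values.

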8.1 Study design

Retrospective observational monocentric study, aimed to investigate the natural history of a rare disease like the LGMD 2E

8.1.1 Primary endpoints

To describe the natural history of the LGMD 2E

To define of the clinical variables that more strongly relate with the evolution of the disease

To identify any possible correlation between variables

To identify any possible correlation between variables and clinical outcomes

To identify any possible correlation between phenotype and genotype

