Loss of independent ambulation* Calf hypertrophy (Unilateral/Bilateral, if bilateral → Symmetrical/Asymmetrical)* Calf atrophy: Unilateral/Bilateral, if bilateral → Symmetrical/Asymmetrical)* Tendon contractures* Scoliosis Scapular winging* Tiptoe gait pattern* Muscle pain* Muscular trophism* Muscular weakness (Symmetrical/Asymmetrical - Proximal/Distal - Progression: chronic/acute)* Muscle contractures (Unilateral/Bilateral - site*

Cramps: Severity – Frequency)* Clubfoot (Unilateral/Bilateral)* Spine anomalies* Ability to walk on toes* Fasciculations* Percussion induced muscular contractions* Macroglossia (yes/no)* Dysphagia(yes/no, Data onset, Progression chronic/acute, Severity-> light/moderate/severe, frequent aspirations:yes/no)

4) Muscles involved: shoulder* arms* forearms* hand* spine* pelvic muscles* thigh* leg* feet

5) Wheelchair: yes/no; if yes → changed through the years – still using yes/no – how long*-other ambulatory devices yes/no; if yes → name → still using yes/no – how long – has it been changed through the years?

6) Deambulation and motility: general comments* Electromyography*

Cardiovascular

1) Evaluations (data): general conditions: using devices to support heart function (eg. pacemakers, ICD, etc.) - name* still using? – How long? - has it been changed through the years?

2) Conduction system anomalies:

EKG * Holter EKG* Echocardiogram* events monitoring*

3)Cardiomyopathy* Heart RM*

4) Symptoms: basal rattling* Oedemas* slopes edemas * Holter* Echocardiogram: Description* FE* Left ventricle telediastolic Volume* Left ventricle telediastolic diameter* Ahythmies* Coronaropathy* Valve* Pulmonary hypertension* Palpitations* Syncope* almost syncope*

Respiratory

1) Evaluations (data):

2) Respiratory support: Invasive/ Noninvasive* Cough assist* Cough peak* Overnight BiPAP * Other*

3) Respiratory status* Pulsoxymetry/polysomnography (mean SpO2 - SpO2 minimal - FC mean - AHI – ODI – %* MVV – MIP – MEP. Dispnoea: supine position– stress induced – at rest*

4) Quality of sleep: daily somnolence* not restorative sleep* frequent overnight awakening* morning headaches* daily fatigue*

Laboratory Tests

1)Imaging tests (data): RX thorax* RX spine* RM muscle*

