8.4 Data sources

Data used to collect variables will include any clinical document provided by patients or available in our hospital thank to the server of the Unit of Neurology. Only official clinical charts will be considered. Clinical outcomes will be defined as the age of loss of ambulation, the age of introduction of cardiological supporting drugs and the age of introduction of respiratory supporting devices/therapies. These ages will be directly obtained from the clinical reports (on report it is reported the age of the patient) of indirectly (according to the data of the report that describes the first introduction of the drug/devices or that firstly reports the loss of the ambulation)

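### The primary screen of variables against milestone ages admits items that encode the milestone and values recorded after it, so a marker that only registers the event can outrank a true early marker

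*Protocol*

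**What the plan says.** Section 8.1.1 lists among the primary endpoints "To identify any possible correlation between variables and clinical outcomes", and 8.7.1 repeats this as an analysis task. The outcomes are fixed in 8.4: "Clinical outcomes will be defined as the age of loss of ambulation, the age of introduction of cardiological supporting drugs", followed by the age at which respiratory devices or therapies are introduced.

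The candidate set is open. Section 7 states: "In this study any investigation performed in patients affected by LGMD 2E will be considered". The list in 8.3 includes:

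- for ambulation: "Loss of independent ambulation", "Wheelchair: yes/no; if yes", and a 10m Walk scale whose last grades are "6 not walking but stands- 7 wheelchair";
- for the respiratory outcome: invasive or noninvasive support, cough assist and overnight BiPAP;
- for the cardiac outcome: therapy by name and date, which would capture cardiological drugs.

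Three rules restrict which values are used. Data must predate the recruiting visit (8.3). Correlation analyses use yearly visits, with a minimum of two values over two years (8.5). Data are divided by age at evaluation (8.7). None of them refers to the date of the milestone.

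Section 8.7.2 says how the results will be used: to choose follow-up variables, to support prompt action, and to identify examinations that can be considered useless.

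**The concern.** Two features combine. First, some candidate variables are the outcome under another label, so their correlation with it is uninformative. Second, a variable that changes because the milestone has happened will correlate with the age at which it happened, since patients with early loss contribute more post-loss values. This occurs even if the variable says nothing beforehand.

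The cost falls on 8.7.2. A test that only records that the patient is already in a wheelchair could be kept as a leading follow-up variable, while a modest but real early marker drops down the list and may be called useless.

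**Working it through.** **No plan figure to reproduce.** The expected cohort of 33 (8.5) is a head count of patients followed over ten years, with no alpha, power or effect size. The check is structural, followed by an illustration of size.

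**Step 1: lists side by side.** Each of the three outcomes in 8.4 has at least one counterpart in 8.3 (see above). No sentence removes a counterpart from the screen against its own outcome, and no rule is tied to the milestone date.

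**Step 2: why it biases.** Let L be a patient's age at the milestone. Let the marker at a visit be X = b + e + δ·1(age ≥ L), with b and e independent of L. This is a null marker that shifts by δ after the event.

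- Patient means: mean X = b + mean e + δ·f, where f is the share of visits after the event. f falls as L rises, so cov(mean X, L) = δ·cov(f, L) < 0.
- One fixed age a: cov(X, L) = δ·cov(1(L ≤ a), L), which is negative whenever some but not all patients have reached the milestone by age a. Dividing by age therefore does not remove the bias.

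Hand check at a = mean of L, with L normal, SD(b) = 1 and SD(e) = 0.5 (assumed):

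r = -δ·0.3989 / √(1 + 0.25 + 0.25·δ²)

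| δ | calculation | r |
|---|---|---|
| 1 | -0.399/√1.50 | -0.33 |
| 2 | -0.798/√2.25 | -0.53 |
| 3 | -1.197/√3.50 | -0.64 |

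For the event indicator itself (wheelchair yes/no), r = -0.3989/0.5 = -0.80.

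**Step 3: simulation.** 33 patients come from 8.5. The rest is assumed: age at loss Normal(14, 4) with a floor of 5; ten yearly visits starting at age 4 to 14; SDs as above; a true marker with latent correlation 0.3 or 0.5 with L; 2000 runs per setting.

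| Null marker, all records | δ = 1 | δ = 2 | δ = 3 |
|---|---|---|---|
| mean r, patient means | -0.25 | -0.44 | -0.55 |
| mean r, adjusted for age at evaluation | -0.23 | about -0.40 | -0.49 |
| mean r, ages 12-16 only | -0.34 | -0.57 | -0.69 |
| p < 0.05, ages 12-16 | about 51% | 97% | 100% |
| outranks true r = 0.3 (age-adjusted) | 44% | 77% | 92% |
| outranks true r = 0.5 (age-adjusted) | 14% | 38% | 64% |

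Wheelchair status itself gives r of about -0.88 within ages 12-16.

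**Step 4: pre-milestone values only.** The null marker's mean r falls to about 0.00 in every setting. At δ = 2 its chance of outranking the true marker falls from 77% to 35% (true r 0.3) and from 38% to 15% (true r 0.5). About 28 of 33 patients (85%) keep at least one value.

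**Step 5: a date filter alone is not enough.** Suppose a marker worsens with age equally in everyone: X = b + β·age + e, unrelated to L. Its pre-milestone mean contains β × (mean age before L), which rises with L. Assumed inputs: 33 patients, age at loss with mean 13 and SD 2 to 4, yearly visits over ages 5-20, 8-14 or 8-18, β of 0.3 to 0.5 SD per year. Pre-loss patient means then correlate with L at about +0.18 to +0.64 and are significant in 18% to 99% of runs; unfiltered means give about 0 and about 5%. Adjusting the pre-milestone values for age at evaluation, or comparing patients at a common landmark age, brings mean r back to about 0, with no more than about 5% significant.

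**The case against.** **Section 8.3 is a collection form, not a list of predictors.** The ambulation, respiratory and therapy items have to be collected because 8.4 derives the outcome ages from them. A reader might infer that the protocol announces a correlation of wheelchair status with age at loss of ambulation. It does not say so. The overlap follows from an unrestricted use of variables in 8.1.1 and 8.7.1, and an analysis plan not shown here could narrow it. This tempers the point without removing it: the protocol itself fixes the outcomes, the open candidate set and the data window.

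**The endpoint speaks of correlation, not prediction.** A reader might take "it will be possible to recognize those patients that are more at risk to develop a more severe disease" (section 6) as the aim of this screen. That sentence concerns the phenotype-genotype study, and genotype precedes any milestone. The decision use rests on 8.7.2.

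**Post-milestone values are legitimate in a natural-history study.** This stands in full for description. It does not justify using them to rank variables against the age at the milestone.

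**Age is already handled in 8.7.** Dividing by age weakens the distortion in some age ranges, but Steps 2 and 3 show that it remains wherever some patients have passed the milestone and others have not.

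**Conclusion.** The point holds as a design fault in the screen against outcomes, and it should be corrected. Under the stated assumptions a null marker with a post-loss shift of 1 to 3 SD reaches an age-adjusted r of roughly -0.2 to -0.5. It outranks a true r = 0.3 marker in 44% to 92% of runs. With a small shift (1 SD) and a strong true marker (r = 0.5) the correction barely alters the ranking: 14% either way.

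A reader might infer that correlations near -0.9 are typical. Values of -0.84 to -0.96 do arise, but only for an item that is noise (grades 1 to 5) before loss and becomes grade 7 after it, averaged over all ages with mean loss age 13 and SD 2 to 4. That ignores the age division in 8.7. At single ages the same item gives about 0 to -0.2 at age 6, -0.3 to -0.6 at age 10, and a peak near -0.7 at ages 12 to 14. These figures apply to items that encode the outcome and say nothing about CK or strength. None of the effect sizes comes from the protocol.

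**What to change.** Amend 8.7.1 as follows.

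1. For each outcome, exclude from the candidate correlates the items that define or encode it. For ambulation: 10m Walk grades 6-7, wheelchair and loss-of-ambulation items. For the respiratory outcome: respiratory support, BiPAP and cough assist. For the cardiac outcome: dated cardiological therapy.
2. Relate other variables to a milestone using only values dated before it. Either adjust for age at evaluation, or compare patients at a common landmark age among those who have not yet reached the milestone. A time-to-event model is an alternative, with patients who have not reached the milestone censored.
3. Keep post-milestone values for the natural-history description only.

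The cost is a few sentences and a date filter; 8.4 already takes milestone ages from the ages or dates on the reports. The price is fewer values per patient, and patients with only post-milestone records drop out of that one analysis (about 5 of 33 under the assumptions in Step 3).
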